## **8 DATA HANDLING CONVENTIONS**

### **8.1 MISSING DATA**

#### **8.1.1 Imputation of Non-Date Missing Data**

Unless otherwise explicitly specified, missing data will not be imputed, and analyses will be based on non-missing values.

Missing data occur when any requested data is not provided, leading to blank fields on the collection instrument. These data will be indicated by a “blank” in subject listing displays.

All available time to progression or death data will be analyzed using appropriate statistical methods that allow for censoring when no progression or death is reported; therefore, subjects with shorter treatment and follow-up due to the natural history of their disease, or medical necessities of the treatment of their disease, will not be considered to have missing time to progression or death data. Subjects with premature study withdrawal (including loss to follow-up) will be included in all analyses for which they have relevant data and for which they are in the analysis set of interest. Subjects who are randomized but are not treated will be censored on study day 1.

For variables which determine the proportion of responses using RECIST v1.1, all subjects in the ITT Analysis Set will be included in the denominator when calculating the percentages; that is, missing response data will be imputed as “no response”.

Subjects with the designation of treatment relationship for AEs and serious adverse events (SAEs) missing will have the worst case assumed to impute the relationship: if relationship to study treatment is missing, it will be assumed to be “Related”.

Idera Pharmaceuticals, Inc.  
Statistical Analysis Plan  
Protocol Number: 2125-MEL-301

---

AEs with a completely missing start date will be assumed to be treatment emergent unless the AE end date is before the date of the first dose of study treatment.

Missing laboratory, vital, and other safety assessment values will not be imputed.

Missing QoL PRO data will not be imputed. At the time of development of this SAP, it is noted that some subjects under protocol version 1 collected QoL data on paper and/or a mixture of paper and electronic media. The handling of mixed modality in the analysis is described in [Section 13](#).

There will be no other imputation for missing data other than as described in [Section 8.1.2](#) for partial dates and times.

In the event that the study is terminated, all available data will be listed and some selected analyses may be performed.

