6. STUDY ENDPOINTS

6.1. Primary Endpoint Family

The primary endpoint family (see [FDA Guidance for Industry, 2017](#)) includes:

- ORR by blinded independent review using RECIST v1.1
- OS, defined as the time to death from any cause measured from the date of randomization.

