15.4.1.2. Primary Analysis of Overall Survival

Overall survival, defined as the time in months from randomization to death from any cause, will be analyzed using the Kaplan-Meier method after approximately 392 deaths have occurred, or approximately 36 months after the last subject is randomized, whichever occurs first. Sensitivity analyses will be detailed in the SAP.

The study hypotheses will be tested using a one-sided, stratified log-rank test. If the null hypothesis is rejected at the appropriate alpha level in accordance with the fallback method, it will be concluded that OS in the IMO-2125 + ipilimumab combination arm is statistically significantly superior to the OS in the ipilimumab alone arm.

Stratification factors will include duration of prior anti-programmed death receptor-1 (PD-1) therapy (≥ 12 weeks vs < 12 weeks), metastasis stage (M1c vs other), and BRAF mutation status and prior targeted therapy (BRAF wild type, BRAF mutation positive with prior targeted therapy, or BRAF mutation positive with no prior targeted therapy) using block randomization. Targeted therapy is the use of an approved BRAF or MEK inhibitor alone or in combination. Stratification will use block randomization. Depending on the distribution of the strata with the ITT, strata may be collapsed as appropriate. The full details will be specified within the SAP.

Subjects who have not died or who are lost to follow up at the data cut-off date will be censored at the last date they were known to be alive.

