### **8.1.2 Imputation of Partial Dates**

Imputed dates will not be used to derive study day, durations (e.g., duration of adverse events), or elapsed time variables. In addition, imputed dates are not used for deriving the last contact date for overall survival.

Partial date imputation will follow Analysis Data Model (ADaM) conventions. The ADaM approach is to populate the numeric date variables with the imputed date and add a flag variable to the dataset that indicates the level of imputation.

The flag variable can contain the values: blank, 'D', 'M', 'Y'.

blank: indicates that no imputation was done

D = 'Day': indicates that the day portion of the date is imputed

M = 'Month': indicates that the month and day portions of the date are imputed

Algorithms for imputing partial dates for AE are as below:

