### **8.2.3 Study Day for Efficacy**

If the date of interest occurs on or after the efficacy reference date, then the efficacy study day will be calculated as (date of interest - efficacy reference date) + 1. If the date of interest occurs prior to the efficacy reference date, then efficacy study day will be calculated as (date of interest – efficacy reference date). There is no efficacy study day 0. Subjects randomized and not treated will be censored at study day 1.

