### 10.1.3 Analysis of OS

The analysis of OS will be performed after 392 deaths or approximately 36 months after the last subject is randomized, whichever occurs first. If the test for ORR is significant, based on the fallback method description in [Section 4.5](#), overall survival will be tested using a one-sided, stratified log-rank test with a significance level of 0.025. The same strata used in the stratified analysis of ORR will be employed in the analysis of OS. If the p-value is  $\leq 0.025$ , the null hypothesis will be rejected with the conclusion that OS in the IMO-2125 + ipilimumab combination arm is statistically superior. Otherwise, if the test for ORR is not significant, the overall survival will be tested using a one-sided, stratified log-rank test with a significance level of 0.005. If the p-value is  $\leq 0.005$ , the null hypothesis will be rejected with the conclusion that OS in the IMO-2125 + ipilimumab combination arm is statistically superior.

OS will be summarized with median, first, and third quartiles of Kaplan-Meier estimates with corresponding 95% CIs calculated by the Brookmeyer-Crowley method [[Brookmeyer, 1982](#)] with log-log transformation. Kaplan-Meier estimates and 95% CIs will also be produced at OS landmark time points at 1 and 2 years. The 95% CIs for Kaplan-Meier estimates at each of the OS landmark time points will be calculated using Greenwood's formula with log-log transformation. OS summaries will include the number of subjects at risk, the number of subjects who died, and the number of censored subjects. In addition, the survival follow-up, defined as the duration between the date of randomization and the date of last contact, in months will be analyzed by reverse Kaplan-Meier method, median and its corresponding 95% CI will be summarized. The figure will identify the number of subjects at risk at each scheduled visit and censored times on the curve. The HR and a 95% CI will be estimated using a Cox proportional hazards model, stratified by the same strata used in the analysis of ORR.

The following table and figure will be provided for OS:

- Overall Survival
- Kaplan-Meier Plot of Overall Survival

The following efficacy listing will be provided:

- Overall Survival

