#### **10.1.5 Sensitivity Analysis of Overall Survival using Imputed Death Dates**

As up to 10% of the enrolled subjects are anticipated to withdraw from the study early, a sensitivity analysis of OS will be performed where the missing death dates are imputed as the last known alive date +1 for the early withdrawn subjects. Results will be summarized with median, first, and third quartiles of Kaplan-Meier estimates with corresponding 95% CIs calculated by the Brookmeyer-Crowley method with log-log transformation. The HR and a 95% CI will be estimated using a Cox proportional hazards model, stratified by the same strata used in the analysis of ORR.

The following summary will be provided:

- Overall Survival Using Imputed Death Dates

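### The SAP censors randomized-but-untreated subjects at study day 1 without limiting this to PFS; applied to OS, it conflicts with the protocol's censoring rule

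*SAP*

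**What the plan says.** The day-1 rule appears twice in the SAP. Section 8.1.1 has "Subjects who are randomized but are not treated will be censored on study day 1", and Section 8.2.3, on efficacy study day, has "Subjects randomized and not treated will be censored at study day 1". SAP Section 8.2.1 makes randomization the efficacy reference date, so efficacy day 1 is the day of randomization.

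Other SAP text points to ordinary OS censoring:

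- The 8.1.1 paragraph that ends with the day-1 sentence begins with all available progression or death data, and with methods that "allow for censoring when no progression or death is reported".
- Section 8.1.2: "imputed dates are not used for deriving the last contact date for overall survival".
- Section 10.1.3 summarizes "the survival follow-up, defined as the duration between the date of randomization and the date of last contact", but does not say how OS is censored.
- Section 10.1.5 is a sensitivity analysis in which "missing death dates are imputed as the last known alive date +1 for the early withdrawn subjects".

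The protocol is clear. Section 6.1 lists "OS, defined as the time to death from any cause measured from the date of randomization". Under Section 15.4.1.2, anyone still alive or "lost to follow up at the data cut-off date will be censored at the last date they were known to be alive". There is no exception for untreated subjects. SAP Section 6.2 analyzes the ITT set as randomized whatever treatment was received, and SAP Section 5 declares no departure from the protocol.

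**The concern.** The rule can be applied to OS in two ways.

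- **Literal:** every untreated subject contributes one day and no event, so recorded deaths leave the ITT test.
- **Milder:** untreated subjects' deaths count, but those without a reported death are cut back to day 1, so known survival time is lost.

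OS is a primary endpoint and the trial is open-label. Failure to start treatment can therefore depend on the assigned arm and on prognosis, and the two readings can move the OS result in different directions. Under the literal reading the trigger and the test also disagree: 392 deaths among randomized subjects start the analysis, but fewer enter it.

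No stated sensitivity analysis restores the data. The Full Analysis Set requires at least one dose, and the Per Protocol set is drawn from it. The unstratified, weighted log-rank and restricted-mean analyses use the ITT set with no different censoring stated. Section 10.1.5 imputes only missing death dates of early withdrawals.

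**Working it through.** **1. The plan's own figure.** Inputs from SAP Section 4.5: HR 0.677, one-sided alpha 0.005, 90% power, 1:1 allocation. Events = 4(z₁₋α + z₁₋β)² / (ln HR)² = 4 × (2.5758 + 1.2816)² / 0.3901² ≈ 391.1, rounded up to 392. The stated figure is reproduced.

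**2. Power under the literal reading.** The untreated rate is not in the documents; 1–5% is assumed, dying in proportion. Deaths lost: 0.01 × 392 ≈ 4 to 0.05 × 392 ≈ 20, leaving 388 to 372. Power = Φ(|ln HR|·√D/2 − z₁₋α):

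| Deaths in test | HR 0.677, alpha 0.005 | HR 0.72, alpha 0.025 |
|---|---|---|
| 392 | 90.1% | 90.2% |
| 388 | 89.7% | 89.9% |
| 372 | 88.2% | 88.6% |

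**3. Type I error by simulation.** From the documents: 454 subjects 1:1, median 11.4 months, 20 months' uniform accrual, 10% drop-out, cut at 392 deaths or 56 months. Assumed: exponential survival, no drug effect, losses at a uniform time in 0–36 months, and untreated subjects drawn at random from a 10% subgroup with death hazard ×1, ×2 or ×3. Test: unstratified one-sided log-rank. There were 60,000 trials per scenario (Monte Carlo SE 0.0006 at 0.025), and all three rules were applied to the same data. Rejection rates at nominal 0.025, with untreated subjects fully followed:

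| Untreated A / B | Hazard | Protocol | Literal | Milder |
|---|---|---|---|---|
| 3% / 3% | ×2 | 0.0253 | 0.0258 | 0.0254 |
| 3% / 3% | ×3 | 0.0257 | 0.0254 | 0.0257 |
| 1% / 3% | ×2 | 0.0251 | 0.0312 | 0.0246 |
| 1% / 3% | ×3 | 0.0260 | 0.0353 | 0.0259 |
| 1% / 5% | ×1 | 0.0244 | 0.0247 | 0.0189 |
| 1% / 5% | ×2 | 0.0260 | 0.0406 | 0.0246 |
| 1% / 5% | ×3 | 0.0250 | 0.0478 | 0.0248 |
| 5% / 1% | ×1 | 0.0258 | 0.0256 | 0.0330 |
| 5% / 1% | ×2 | 0.0262 | 0.0151 | 0.0274 |
| 5% / 1% | ×3 | 0.0253 | 0.0125 | 0.0256 |

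Under the literal reading at ×2–3, the average HR is 0.98–0.97 for 1% / 5% and 1.02–1.03 for 5% / 1%. Under the milder reading at ×1 it is 1.01 and 0.99. At nominal 0.005 (1% / 5%, ×3), the three rules give 0.0050, 0.0110 and 0.0050. With 3% untreated, about 379 deaths enter the literal test, against 392 under the other two rules.

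The milder reading changes little at ×2–3 because nearly all such subjects die before the cut. With average prognosis (×1) the literal reading is harmless and the milder one shifts.

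**4. Dependence on follow-up.** If half the untreated leave at day 1 (×2–3), the protocol rule itself gives 0.032–0.034 for 1% / 5% and 0.019–0.018 for 5% / 1%. The literal reading gives 0.040–0.047 and 0.014–0.012. If all leave (20,000 trials), protocol and literal give 0.0388 and 0.0390 at ×2, and 0.0482 and 0.0483 at ×3, for 1% / 5%: agreement within 0.0002.

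**The case against.** The strongest reply is that PFS was meant. Time to progression or death resembles the SAP's PFS definition, and the PFS table in SAP Section 16.4 has no row for untreated subjects, a gap that a day-1 rule would fill. The OS-specific text uses last contact and last known alive, as the protocol does. The literal reading also clashes with the opening of its own paragraph, with the ITT definition and with the 392-death trigger. SAP Section 8.2 adds that separate dataset specifications hold the full derivations, and these are not available here. This makes PFS a plausible intent, and deletion of deaths is one reading, not an established plan. But no SAP sentence exempts OS from a rule stated twice.

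The second reply is about size. The larger shifts need the literal reading, a marked imbalance, poor prognosis and continued follow-up all at once. None of these is documented, and first dose is due within 2 days of randomization. A smaller imbalance (1% / 2%, 20,000 trials, SE about 0.001) gives 0.028–0.029 under the literal reading against 0.025 under the protocol rule. The simulated test is unstratified, whereas the planned one is stratified. The large shifts in opposite directions also come from different prognosis assumptions, not from one scenario. These limits stand, and so does one more: for an untreated subject with no contact after randomization, day 1 is the last date known alive and there is no conflict.

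**Conclusion.** The concern holds. The day-1 rule is not limited to PFS, the SAP is inconsistent about whether it reaches OS, and both ways of applying it to OS depart from protocol Section 15.4.1.2 and the ITT principle wherever an untreated subject has survival data after day 1. Confidence in this is high.

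The likely effect is small: under 2 points of power with up to 5% untreated, and no type I error shift from the literal reading when non-treatment is balanced. It becomes material only with imbalance between arms and retained follow-up. Its direction then depends on the reading, on which arm has more untreated subjects and on their prognosis. All untreated rates and hazards are assumptions, so the type I error figures are illustrative. It should still be corrected, because a primary-endpoint censoring rule should not be left to a programmer's choice.

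**What to change.** State in SAP Section 10.1.3 that every randomized subject, treated or not, counts as an OS event at death and is otherwise censored at the last date known alive, as the protocol requires. Remove the day-1 sentences for OS from Sections 8.1.1 and 8.2.3, or limit them to PFS for subjects with no post-baseline tumor assessment and no death, and add that row to the Section 16.4 table.

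Wording cannot recover subjects who leave at day 1, so report the number untreated and their survival follow-up by arm. SAP Section 9.1 already gives analysis-set counts and overall survival follow-up, so this adds only the untreated subset.

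The cost is SAP wording, settled before database lock. Protocol Section 16.1 already requires the full dataset for all randomized subjects.

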### **8.1.2 Imputation of Partial Dates**

Imputed dates will not be used to derive study day, durations (e.g., duration of adverse events), or elapsed time variables. In addition, imputed dates are not used for deriving the last contact date for overall survival.

Partial date imputation will follow Analysis Data Model (ADaM) conventions. The ADaM approach is to populate the numeric date variables with the imputed date and add a flag variable to the dataset that indicates the level of imputation.

The flag variable can contain the values: blank, 'D', 'M', 'Y'.

blank: indicates that no imputation was done

D = 'Day': indicates that the day portion of the date is imputed

M = 'Month': indicates that the month and day portions of the date are imputed

Algorithms for imputing partial dates for AE are as below:

#### **Adverse Event**

Imputations in the adverse events dataset are used for slotting events to the appropriate study time periods and for sorting in data listings. The imputed dates will be used in the derivation of the treatment emergence flag. They will not be used to calculate duration of AEs. If an AE start or end date is partially or completely missing, then the duration of the AE will be set to missing.

Idera Pharmaceuticals, Inc.  
 Statistical Analysis Plan  
 Protocol Number: 2125-MEL-301

Date	Missing Element	Rule
Start Date	day, month, and year	
 
Do not impute completely missing AE start dates
 

	day, month only	
 
If AE start year is same as the year of study start, set to the date of the first dose of study treatment; otherwise,
 
Set to January 1st of the year the AE started
 

	day only	
 
If the AE start year and month are the same as the first dosing date, impute the missing day as the first dosing date; otherwise,
 
Set start date to the 1st of the month the AE started
 

End Date	any date element	
 
No imputation for completely or partially missing AE end dates; as applicable, report the AE as ongoing and the AE duration as missing
 

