### Concomitant Medication

Partial concomitant medication start and end dates will be used to derive the reference variables for concomitant medication start and end relative to treatment; any imputed dates will be included in the analysis dataset with an identifier as imputed. The reference variables will be used to differentiate before, during, and after treatment for the concomitant medication. The imputed dates will not be used to calculate study day or duration.

Date	Missing Element	Rule
Start Date	day, month, and year	
 
If the medication start date is completely missing and the end date is either after the first dose date or completely missing, then set the missing start date as the first dose date.
 

	day, month only	
 
If the medication start year is same as the year of study start, set to the first dose date; otherwise,
 
Set to January 1st of the year the concomitant medication started
 

	day only	
 
If the medication start year and month are the same as the first dose date, impute the missing day as the first dose date; otherwise,
 
Set start date to the 1st of the month the concomitant medication started.
 

End Date	day, month, and year	
 
If the end date is completely missing or Ongoing is checked, set the missing end date as the last contact date.
 

	day, month only	
 
If the partial end date contains year only, set end date to the earliest of December 31st or the last contact date.
 

	day only	
 
If the partial end date contains month and year, set the end date to the earliest of the last day of the end month reported or the last contact date.
 

Idera Pharmaceuticals, Inc.  
Statistical Analysis Plan  
Protocol Number: 2125-MEL-301

---

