## 9.5 CONCOMITANT MEDICATIONS

Concomitant medications will be coded using the World Health Organization (WHO) Drug Dictionary Version B3 Sep 2020. A concomitant medication is defined as any drug or substance administered between the time of the first dose of study treatment and 30 days from the date of the last dose of study treatment, or taken to treat SAEs, irAEs, AEs of Grade 3 or above that occurred within 90 days of the last dose of study treatment, or taken to treat Grade 3 or above treatment-related AEs and SAEs that occurred during either the Active or Survival follow-up periods. This includes medications that were started prior to screening if their use continued during dosing. If the start date or end date of concomitant medication is partial, use the imputation rules defined in [Section 8.1.2](#) to impute the date and determine if the medication was concomitant.

In the summary of concomitant medications, each subject is counted once within each unique term. For example, if a subject takes Amoxicillin on two separate occasions, the subject is counted only once under the ingredient “Amoxicillin”.

The summary of concomitant medications using the Safety Set will show the number and percentage of subjects taking concomitant medications by therapeutic class and preferred term (PT). Anatomical Therapeutic Chemical (ATC) Level 4 will be used for the listing and summary.

Idera Pharmaceuticals, Inc.  
 Statistical Analysis Plan  
 Protocol Number: 2125-MEL-301

A similar summary will also be generated for concomitant medications that were used to treat immune-related adverse event as recorded on the Concomitant Medication eCRF page.

Another summary will be generated by category of concomitant immune-modulating medications that were used to treat irAEs. These medication categories include thyroid hormone replacement therapies, systemic steroids, and immune-suppressants. Thyroid hormone replacement therapies will be identified by WHO drug ATC prefix H03, systemic steroids by WHO drug ATC prefix H02, and immuno-suppressants by WHO drug ATC prefix L04. Any medications with one of these prefixes that were indicated on the Concomitant Medication eCRF page as being used to treat irAEs will be included in this summary by preferred term under the corresponding category.

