## 11 SAFETY ANALYSES

All safety analyses will be based on the Safety Set as defined in [Section 6.5](#). Summaries of AEs will include only treatment-emergent AEs (TEAEs), defined as AEs with a start date on or after the date of first dose of study treatment or existing AEs which increase in CTCAE grade after the start of study treatment. If it cannot be determined definitively whether the AE is treatment emergent due to missing or partial onset or end dates, then it will be counted as treatment emergent (see [Section 8.2.7](#) for details).

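### SAP 8.1.2 moves a partial AE start date to the first dose without checking the recorded end date, so an event that ended before treatment can be flagged treatment-emergent

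*SAP*

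**What the plan says.** **Partial AE starts (SAP 8.1.2, Adverse Event).** When the day is missing: "If the AE start year and month are the same as the first dosing date, impute the missing day as the first dosing date". When day and month are missing: "If AE start year is same as the year of study start, set to the date of the first dose of study treatment". Otherwise the start becomes the first of the known month, or 1 January of the known year. The imputed date has a consequence: "The imputed dates will be used in the derivation of the treatment emergence flag".

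**Wholly missing AE starts (SAP 8.1.1).** These events "will be assumed to be treatment emergent unless the AE end date is before the date of the first dose of study treatment". Here the end date is checked.

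**The flag (SAP 8.2.7).** It is derived from the start date. An AE dated on the day of first dose is emergent, with an exception when NOT APPLICABLE was entered as the action taken for both drugs (and similarly in the ipilimumab-alone arm).

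**The default (SAP 11).** "If it cannot be determined definitively whether the AE is treatment emergent due to missing or partial onset or end dates", the event is counted as emergent. The sentence then refers back to 8.2.7.

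**Medications (SAP 8.1.2 and 9.5).** The day-missing row works as for AEs. The year-only row reads: "If the medication start year is same as the year of study start, set to the first dose date". A wholly missing start is moved to first dose only if the end date is after first dose or is also wholly missing. Section 9.5 then applies these rules "to impute the date and determine if the medication was concomitant".

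**Protocol 10.1.2.** AEs are collected from consent, and TEAE summaries are limited to events that began after the first dose.

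**The concern.** The SAP recognises that an end date before first dose settles the question, and it uses that fact when the start date is blank. It does not use it when the start is partly known. A site that writes only the month of onset can thus cause a resolved screening event to be flagged, while a site that writes nothing does not.

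Moving an uncertain start forward to first dose is a usual conservative convention when the event might have begun on treatment. Here it cannot have done so. Counting it conflicts with the protocol's definition of a TEAE and with Section 11's own condition that status be indeterminate. The outputs exposed are the TEAE tables and, less certainly, the concomitant-medication tables. Imputed records can also show a start later than the end.

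**Working it through.** No figure in the plan needs reproducing. The check is to apply the rules as written to records whose end date is complete and falls before first dose.

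**Inputs.** The two partial-start rows for AEs and the two for medications (SAP 8.1.2), the start-date basis of the flag (8.2.7), and the end-date condition for wholly missing starts (8.1.1 for AEs, 8.1.2 for medications). The dates are invented for illustration. In the year-only rows, study start is read as the subject's own first-dose year.

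**Rule as coded.** Month known: start = first dose if year and month match first dose, otherwise the first of that month. Year only: start = first dose if the year matches, otherwise 1 January. On treatment by start date = imputed start on or after first dose.

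| Record | First dose | Imputed start | Imputed start minus recorded end | On treatment by start date | With end-date check |
|---|---|---|---|---|---|
| AE, start Mar-2019, end 10-Mar-2019 | 20-Mar-2019 | 20-Mar-2019 | +10 days | Yes | No |
| AE, start 2019, end 05-Mar-2019 | 20-Mar-2019 | 20-Mar-2019 | +15 days | Yes | No |
| AE, start Feb-2019, end 10-Mar-2019 | 20-Mar-2019 | 01-Feb-2019 | −37 days | No | No |
| Drug, start Mar-2019, end 10-Mar-2019 | 20-Mar-2019 | 20-Mar-2019 | +10 days | Yes | No |
| Drug, start 2019, end 15-Feb-2019 | 20-Nov-2019 | 20-Nov-2019 | +278 days | Yes | No |

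Four of the five pre-treatment records are dated to first dose. None is once the end date is checked. The third row shows that the rule behaves properly when the known month differs from the first-dose month.

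**Side by side.** Take the first AE and erase its start date. Under 8.1.1, the end of 10 March precedes the dose of 20 March, so the event is not emergent. Restore the month and 8.1.2 moves the start to 20 March. Section 8.2.7 then makes it emergent unless the action-taken exception applies. Section 11 would not reach this result by its default, because the end date settles the status, but it refers to 8.2.7, which has no end-date test.

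**Can the case arise?** Yes. AEs are recorded from consent. The schedule notes allow 28 days from consent to randomization and 2 more to first dose, so up to 28 + 2 = 30 days of pre-dose collection.

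**What is insulated.** Under 8.1.2, imputed dates are not used for study day, durations, elapsed times or the last contact date for OS. Section 11.2 drops incomplete onset dates from the 3-week onset table.

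**The case against.** **The same-day exception is a real guard.** NOT APPLICABLE is a natural entry for an event that resolved before any dose, and it would remove the flag. Protocol 10.1.3.7 does not list that category, but the SAP treats it as a recorded value and the eCRF is not available, so one cannot conclude that the form lacks it. This part of the objection stands. The guard is still partial: it depends on a form field rather than on the end date. Its wording is also confused, since a relationship to study drug reads as a second ground for exclusion.

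**For drugs, the recorded end date survives.** A reader might infer that prior drugs enter the concomitant tables. The documents do not show that. Section 8.1.2 derives both a start and an end variable relative to treatment, and 9.5 admits drugs begun earlier only if use continued into dosing. A drug that stopped before first dose fails that definition. The SAP does not say which date prevails when the imputed start falls after the end, so miscounting remains possible but unproven.

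**Events losing the flag.** If study start meant the start of the trial, year-only AEs in later-enrolled subjects would go to 1 January, and a reader might infer that they drop out of the TEAE tables. Section 11's default counts events of indeterminate status as emergent, which undercuts that inference. What remains is an undefined phrase.

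**A rate.** With onset uniform over the 28 days before first dose and the dose day d uniform over a 30-day month, the mean of min(d − 1, 28)/28 is 434/840 = 0.517. A reader might take this for a misclassification rate. It is only the share of day-missing screening onsets that fall in the first-dose month under those assumptions. It includes events that continued past first dose and ignores the same-day exception.

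**Separate specifications.** SAP 8.2 leaves full derivations to dataset specifications, which may contain a check that start does not follow end. They cannot be seen, and the algorithm the SAP states gives the wrong result when followed.

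**Conclusion.** The point holds for adverse events. As written, 8.1.2 and 8.2.7 together can flag as treatment-emergent an AE whose recorded end precedes first dose, against the SAP's own treatment of wholly missing starts, the condition in Section 11 and the protocol's TEAE definition. For medications, starts dated after ends follow directly from the rule; miscounting as concomitant is possible only.

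The size cannot be computed from the documents. It depends on how many records combine a partial start in the first-dose month or year with an end before first dose and, for AEs, with no NOT APPLICABLE entry. That number is probably small. The main ORR and OS analyses, study day, durations and the onset-interval table are unaffected. This is a minor correction, worth making because it is cheap and removes an inconsistency in the safety tables.

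**What to change.** 1. In SAP 8.1.2, add one condition to each partial-start row for AEs and medications: if the recorded end date is before first dose, do not move the start to first dose but set it to the first day of the known month or year. Such an AE is not treatment-emergent and such a drug is prior.
2. State the same condition in 8.2.7 and Section 11, so that flag, default and imputation agree. Clarify the same-day exception in 8.2.7 at the same time.
3. In the year-only rows, replace the reference to the year of study start with the year of the subject's first dose.

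The cost is a few sentences and a small programming change. No new data are needed. If the dataset specifications already contain the check, only the SAP text has to be brought into line.
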